### 8.3.2.3 Secondary Endpoint 3 – CNC Words

The secondary endpoint 3 will be assessed with the following hypothesis:

 $H_0:\Delta\leq 0$ 

 $H_a: \Delta > 0$ 

where  $\Delta$  represents the difference between baseline unaided speech perception CNC and 6 months-post surgery CNC, specifically  $\Delta$  = CNC6 Months – CNCpreop. This difference is parameterized so that a positive value is indicative of a clinical improvement.

The hypothesis will be evaluated using a one-sample, one-sided 0.025 alpha level t-test for a mean against the null of zero. The objective will be met if the null hypothesis is successfully rejected.

The endpoint will be presented with descriptive statistics and the corresponding two-sided 95% confidence interval based on the t-distribution.

### 8.3.2.4 Secondary Endpoint 4 – BKB-SIN

The secondary endpoint 4 will be assessed with the following hypothesis:

 $H_0:\Delta\leq 0$ 

 $H_a: \Delta > 0$ 

where  $\Delta$  represents the difference between baseline unaided speech perception BKB SIN test and 6 monthspost surgery BKB SIN test, specifically  $\Delta$  = BKB6 Months – BKBpreop. This difference is parameterized so that a positive value is indicative of a clinical improvement.

The hypothesis will be evaluated using a one-sample, one-sided 0.025 alpha level t-test for a mean against the null of zero. The objective will be met if the null hypothesis is successfully rejected.

The endpoint will be presented with descriptive statistics and the corresponding two-sided 95% confidence interval based on the t-distribution.

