### 6.3.2.2.2 Bramford-Kowal-Bench Speech-In-Noise (BKB-SIN)

BKB-SIN (Etymotic Research, 2005) is composed of 36 lists of BKB sentences (Bench, Kowal, & Bamford, 1979), spoken by a male target talker amidst four-talker babble. The 36 lists are divided into 18 equally difficult pairs of sentence lists. The list-pairs are composed of 16 to 20 sentences that each have 3 or 4 key words. Target speech is presented at 65 dBA and the level of the noise is varied in 3 dB steps at fixed SNRs, beginning at +21 dB SNR (very easy), and descending to 0 or –6 dB SNR (very difficult), depending on the list. Speech reception threshold (SRT) is calculated in dB, which is referred to as the SNR-50, is defined as the signal-to-noise ratio (SNR) required for the subject to repeat 50% of the key words correctly. One list pair of sentences will be presented at 0° azimuth in the sound field, with babble presented at 0° azimuth (SON0). Preoperatively, BKB-SIN will be assessed in the unaided condition as well as the aided condition using the Baha 5 Power on a softband. Postoperatively, BKB-SIN will be assessed only in the aided condition using the Osia 2 sound processor. Pre and postoperative testing will be completed with the contralateral ear plugged or muffed in an effort to isolate the treated ear.

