#### 5.6.5 Secondary Endpoint 4 – BKB SIN

Secondary endpoint 4 is defined as the mean difference between baseline unaided speech perception in quiet and the aided condition using the Osia 2 system at 6 months post-surgery on an adaptive speech in noise test BKB SIN.

### 5.6.5.1 Primary Analysis of Secondary Endpoint 4

The secondary endpoint 4 will be assessed with the following hypothesis:

 $H_0$ :  $\Delta \leq 0$ 

 $H_a$ :  $\Delta > 0$ 

where  $\Delta$  represents difference between baseline unaided speech perception BKB SIN test and 6 monthspost surgery BKB SIN test, specifically  $\Delta = BKB_{6 \, Months} - BKB_{preop}$ . This difference is parameterized so that a positive value is indicative of a clinical improvement.

The hypothesis will be evaluated using a one-sample, one-sided 0.025 alpha level t-test for a mean against the null of zero. The objective will be met if the null hypothesis is successfully rejected.

The endpoint will be presented with descriptive statistics and the corresponding two-sided 95% confidence interval based on the t-distribution.

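### The BKB-SIN test (secondary endpoint 4) points the wrong way: SNR-50 falls when hearing improves, but the objective is met only if it rises

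*Protocol*

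**What the plan says.** Protocol 6.3.2.2.2 describes the score. Speech is presented at a fixed level and the noise varies in 3 dB steps, "beginning at +21 dB SNR (very easy), and descending to 0 or –6 dB SNR (very difficult") depending on the list. The result is the SNR-50 in dB, "defined as the signal-to-noise ratio (SNR) required for the subject to repeat 50% of the key words correctly".

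Protocol 8.3.2.4 sets the hypothesis. Δ is "BKB 6 Months – BKB preop", with H0: Δ ≤ 0 and Ha: Δ > 0. It then states: "This difference is parameterized so that a positive value is indicative of a clinical improvement". The test is a one-sample t-test against zero at one-sided 0.025, and the objective is met if H0 is rejected.

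SAP 5.6.5.1 repeats the formula, the hypotheses and the sentence on sign. It describes Δ in words as the "difference between baseline unaided speech perception BKB SIN test and 6 monthspost surgery BKB SIN test". The endpoint definition at the head of SAP 5.6.5 calls the comparison the "mean difference between baseline unaided speech perception in quiet and the aided condition", whereas protocol 8.2.2.4 says the baseline is in noise.

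**The concern.** SNR-50 is a threshold: it is the signal-to-noise ratio that the child needs. The protocol labels high ratios easy and low ratios difficult, so reaching 50% correct at a lower ratio is better performance. Subtracting baseline from follow-up makes improvement negative. The alternative Δ > 0 is then the hypothesis that speech in noise got worse.

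The same form is correct for CNC words (protocol 8.3.2.3), which are scored as percent correct. It does not carry over to a score where lower is better.

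At stake is a formal test meant to support a labelling claim (protocol 8.1, SAP 5.6). Followed literally, a device that helps fails this objective and a device that harms hearing in noise meets it. If the contradiction is noticed only after the data are in, someone has to choose the direction of a one-sided hypothesis post hoc, in an open-label study.

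**Working it through.** **Inputs**
- n = 50 (protocol 8.4, SAP 4).
- One-sample t-test, one-sided α = 0.025, H0: Δ ≤ 0 (protocol 8.3.2.4, SAP 5.6.5.1).
- Δ = 6-month minus preoperative score (same sections).
- Score = SNR-50 in dB, lower is better (protocol 6.3.2.2.2).
- Effect size: neither document gives a BKB-SIN effect or SD. Below, d is the true fall in SNR-50 divided by the SD of the paired difference. The values of d are assumptions.

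**The plan's own figures, reproduced**
- CI half-width: t(0.975, 49)/√50 = 2.0096/7.0711 = 0.2842. The plan states 0.284.
- Chance of at least one event at a 5.9% rate: 1 − 0.941^50 = 95.2%. The plan states more than 95%.

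**Direction, on one child (assumed scores)**
Unaided SNR-50 of 10 dB before surgery and aided SNR-50 of 5 dB at 6 months is an improvement. The written formula gives Δ = 5 − 10 = −5, which lies in H0.

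**What rejection requires as written**
Reject when mean(Δ)/(SD/√50) > 2.0096, that is, when mean(Δ) > 0.284 SD. The observed mean SNR-50 must have risen by more than 0.284 SD.

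**Chance of meeting the objective**
The t statistic has a noncentral t distribution with 49 degrees of freedom. Its noncentrality is −d√50 as written and +d√50 with the direction corrected. At d = 0.5 these are −3.54 and +3.54.

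| True change in SNR-50 | As written | Direction corrected |
|---|---|---|
| Improves 0.2 SD | 0.04% | 28.3% |
| Improves 0.3 SD | 0.003% (2.7 × 10⁻⁵) | 54.8% |
| Improves 0.5 SD | 2.8 × 10⁻⁸ | 93.4% |
| Improves 1.0 SD | about 3 × 10⁻¹⁹ | > 99.9% |
| No change | 2.5% | 2.5% |
| Worsens 0.5 SD | 93.4% | 2.8 × 10⁻⁸ |

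Simulation of 200,000 trials per effect size agreed: at d = 0.2, 0.04% as written and 28.3% corrected; at d = 0.5, 0% and 93.3%.

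**Sensitivity to missing pairs**
With 40 complete pairs, the corrected test has 45.6% power at d = 0.3 and 86.9% at d = 0.5. The written test has 6.9 × 10⁻⁵ and 2.2 × 10⁻⁷. The direction of the problem does not depend on n.

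**The case against.** The strongest reply is that the intended direction is in the text. The sentence on sign says positive means improvement, so the documents conflict with themselves rather than plainly adopt a reversed test, and a competent analyst would see it. The two-sided 95% confidence interval and descriptive statistics are also reported, so a reversed result would be visible. This is fair as to intent. It does not remove the problem: the formula is explicit, both documents carry it, and success is decided by the one-sided rejection and not by the interval.

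A second reply concerns scope. Testing stops at the first non-significant result, and BKB-SIN is numbered fourth. If the order follows the numbering, the probabilities above apply to a formal claim only when SSQ, PTA and CNC have all passed. That condition stands. It also exposes a linked issue: PTA (protocol 8.3.2.2, SAP 5.6.3.1) uses the same follow-up-minus-baseline form on a dB threshold, where lower is again better. Correcting BKB-SIN alone may therefore not be enough for its formal test to be reached.

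Third, this is one secondary endpoint. The primary endpoint is safety with no hypothesis test, and the sample size is not power-driven. That limits the damage to this claim but does not make the rule for the claim correct.

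The reference to quiet in SAP 5.6.5 is a separate slip. The same sentence names a speech-in-noise test, so it adds no weight to the reversal.

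**Conclusion.** The concern holds: the success rule for secondary endpoint 4 is wrong as written in both documents. It follows from the protocol's own definition of SNR-50 and needs no outside source.

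Read literally, the objective can be met only when the observed mean SNR-50 worsens by more than 0.284 SD, which happens 2.5% of the time by chance if nothing has changed. The loss is close to total for any plausible benefit. The sizes rest on assumed standardized effects, 50 complete pairs and this test considered alone, before any gatekeeping condition. The direction of the error rests on none of these. It must be corrected before the analysis.

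**What to change.** - In protocol 8.3.2.4 and SAP 5.6.5.1, define Δ = BKB preoperative (unaided) − BKB at 6 months (aided). H0: Δ ≤ 0, Ha: Δ > 0 and the sentence on sign can then stay as they are.
- If the present difference is kept instead, the hypotheses must become H0: Δ ≥ 0 and Ha: Δ < 0, and the sentence must say that a negative value is improvement. Changing Ha alone is not enough.
- In SAP 5.6.5.3, tie the conditional Sign test to the corrected Δ, and state that best means the largest fall in SNR-50 and worst the smallest fall or largest rise. The tipping-point analysis already runs every combination, so this affects its reading, not its numbers.
- In SAP 5.6.5, change the baseline description from quiet to noise, to match protocol 8.2.2.4.
- Check the sign for PTA in protocol 8.3.2.2 and SAP 5.6.3.1 at the same time.

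**Cost.** This is a wording correction, with no new data, visits or subjects and no change in sample size or precision. It needs a protocol amendment with the agreement and notifications in protocol 17, and an approved SAP amendment under SAP 6. Both should be complete before the 6-month lock in protocol 13.3, so that the direction is not chosen after the results are known.

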### 8.3.3 Exploratory Hypothesis

There are no exploratory hypotheses.

## 8.4 Sample Size Determination

Sample size for the study is not driven by power requirements for a formal statistical hypothesis test. The planned sample size of 50 subjects will provide data to characterize safety and effectiveness with a reasonable degree of statistical precision. Additionally, the planned sample size will allow for a high probability of observing events of interest. For example, with 50 subjects, the half-width of a two-sided 95% confidence interval for a continuous endpoint based on a t-distribution would be 0.284 units on the effect size scale. Similarly, with 50 subjects, there is a greater than 95% probability of observing one or more events that occur at a population rate of 5.9%.

Stratification of the 50 subjects will include a minimum of 10 subjects with single-sided-deafness. In addition, at least one-third (15) of the subjects represented at the youngest ages (5-6 years) will be implanted with the remaining 35 subjects represented by the other age groups as evenly as possible.

## 8.5 Analysis Populations

Analysis will be based on subjects who are successfully implanted with the device.

## 8.6 Endpoint Analyses

### 8.6.1 Primary Endpoint Analyses

There is no formal hypothesis test for the primary endpoint.

The endpoint will be presented in tabular format, displaying the number and percentage of subjects with adverse events. Events will also be summarized by type and severity. Results will be based on observed events without imputation.

### 8.6.2 Secondary Endpoint Analyses

The secondary endpoint (1 - 4) analyses will be presented with descriptive statistics and the corresponding two-sided 95% confidence interval based on the t-distribution.

### 8.6.3 Exploratory Endpoint Analyses

There are no exploratory endpoints.

## 8.7 Safety Analyses

Adverse events (AEs) will be tabulated with the number of events and subjects with event for each event type and overall. Rates will be reported as the number of subjects who experience at least one event during the analysis interval out of the total number of subjects with follow-up to the beginning of the analysis interval. Serious adverse events (SAEs) will also be tabulated.

All AEs and SAEs will also be summarized by relatedness as described above. Adverse events leading to death or study discontinuation will be provided in listing format.

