### 8.2 Endpoints

### 8.2.1 Primary Endpoint

The primary endpoint is adverse events and serious adverse events Surgery through Visit 4 (6 Months). Events will be summarized by type, frequency, and severity.

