### 8.3 Hypotheses

### 8.3.1 Primary Hypothesis

There is no formal hypothesis test for the primary endpoint.

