#### 5.6.1 Primary Endpoint

The primary endpoint is device and procedure related adverse events Surgery through Visit 4 (6 Months). Events will be summarized by type, frequency, and severity.

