## 5.8 Safety Analyses

Adverse events (AEs) will be tabulated with the number of events and subjects with event for each event type and overall. Rates will be reported as the number of subjects who experience at least one event during the analysis interval out of the total number of subjects with follow-up to the beginning of the analysis interval. Serious adverse events (SAEs) will also be tabulated.

All AEs and SAEs will also be summarized by relatedness as described above. Adverse events leading to death or study discontinuation will be provided in listing format.

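### The adverse-event rate counts a child lost early without an event as event-free, so the primary 6-month rate is biased low if such losses occur

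*Protocol*

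**What the plan says.** SAP 5.8 sets the numerator: "Rates will be reported as the number of subjects who experience at least one event during the analysis interval". The denominator follows: "out of the total number of subjects with follow-up to the beginning of the analysis interval". Protocol 8.7 uses the same rule. Neither document defines the analysis interval.

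For the primary endpoint, Protocol 8.2.1 and SAP 5.6.1 both set the period as surgery through Visit 4 (6 months). Protocol 8.6.1 promises a table "displaying the number and percentage of subjects with adverse events" and adds: "Results will be based on observed events without imputation". SAP 5.6.1.1 matches it. Neither section says what the percentage is a percentage of. The population is given in Protocol 8.5: "Analysis will be based on subjects who are successfully implanted with the device".

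No time-to-event, exposure-adjusted or missing-follow-up analysis is described for the primary endpoint. The multiple imputation and tipping-point analyses in SAP 5.6.2 to 5.6.5 cover only the four secondary endpoints.

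**The concern.** The primary objective is to quantify the type, frequency and severity of adverse events, and the 6-month data support the regulatory submission (Protocol 8.8). With an interval that starts at surgery, every implanted child is in the denominator from the first day. A child who leaves event-free at week 3 contributes three weeks of observation but is counted as if observed event-free for six months. When loss is unrelated to events, this error can only lower the reported rate, which is the direction that favours the device. Unlike sampling error, it would not average out with more subjects. The secondary endpoints have a plan for missing data; the primary safety rate does not.

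**Working it through.** **Inputs.** n = 50 (Protocol 8.4). Interval: surgery to 6 months (Protocol 8.2.1). Population: successfully implanted subjects (Protocol 8.5). The documents give neither a dropout rate nor an expected adverse-event rate. I therefore assume loss d of 0–20% by 6 months and true 6-month risks p of 5.9% (the rate used in the sample-size section), 20% and 50%.

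**The plan's own figure.** Protocol 8.4 claims a better than 95% chance of seeing at least one event that occurs at a 5.9% rate: 1 − 0.941^50 = 0.952. This reproduces. It assumes that all 50 are followed; with 45 it is 1 − 0.941^45 = 0.935.

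**Expected crude rate when loss is unrelated to events.**

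(a) Constant hazards. Let L = −ln(1−p) and G = −ln(1−d) be the cumulative event and dropout hazards over 6 months. The expected crude rate is [L/(L+G)] × [1 − (1−p)(1−d)]. For p = 20% and d = 10%: L = 0.2231, G = 0.1054, so 0.6793 × (1 − 0.72) = 19.0%.

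(b) The same, with 80% of the cumulative event hazard in month 1.

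(c) The extreme case, with all losses immediately after surgery: p(1−d). For p = 20% and d = 10%: 18.0%.

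| True risk p | Loss d | (a) constant | (b) early events | (c) all lost at once |
|---|---|---|---|---|
| 5.9% | 5% | 5.75% | 5.85% | 5.60% |
| 5.9% | 10% | 5.60% | 5.79% | 5.31% |
| 5.9% | 20% | 5.29% | 5.67% | 4.72% |
| 20% | 5% | 19.5% | 19.8% | 19.0% |
| 20% | 10% | 19.0% | 19.7% | 18.0% |
| 20% | 20% | 18.0% | 19.3% | 16.0% |
| 50% | 5% | 48.9% | 49.6% | 47.5% |
| 50% | 10% | 47.7% | 49.2% | 45.0% |
| 50% | 20% | 45.4% | 48.4% | 40.0% |

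With d = 0 the crude rate equals p in every case.

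**Check with another dropout pattern.** With dropout spread evenly over the 6 months and a constant event hazard, the crude rate is (1−d)p + d × [1 − p/L]. For p = 20% the bracket is 1 − 0.2/0.2231 = 0.1037, giving 19.5%, 19.0% and 18.1% at 5%, 10% and 20% loss. This agrees with (a) to within 0.1 point.

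**Scale.** The exact 95% confidence interval for 10 events in 50 children is 10.0% to 33.7%.

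**Why deleting the lost children is not the remedy.** Suppose 10 children have an event and 5 are lost event-free. The crude rate is 10/50 = 20.0%. Removing the 5 gives 10/45 = 22.2%, which discards event-free time that was observed. Giving them half weight gives 10/47.5 = 21.1%. Counting all 5 as events gives 15/50 = 30.0%.

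**The case against.** The case for leaving the plan alone is substantial. A crude proportion of observed events is a legitimate descriptive summary. Protocol 8.3.1 says: "There is no formal hypothesis test for the primary endpoint". There is also no safety threshold, so no decision can reverse. At 5–10% loss the shift is small beside the width of the interval above. Many of the risks listed in Protocol 7.2 arise from surgery or implantation; if events do come early, the shift is smaller still. All of this stands, and it limits the point to an improvement.

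A reader might infer more than the documents support:

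- **That the primary rate is biased low as planned.** This depends on children being lost within the interval and before any recorded event. With no such loss there is no bias. A child lost before a later interval begins is dropped from that interval's denominator.
- **That the documents fix the primary denominator as every implanted child.** The rule sits in the general safety sections; applying it to the primary endpoint is an inference, though the natural one.
- **That nothing offsets the problem.** Protocol 6.2.5 and 6.2.6 allow continued safety follow-up, with permission, after withdrawal for device safety or performance. SAP 5.4 tabulates accountability by visit and early exits by reason. These are partial remedies: the follow-up is optional and does not reach children lost to contact, and the table shows losses without correcting the rate.
- **That the bias grows whenever children with problems leave.** A child who leaves after a recorded event is already in the numerator. Only loss before the first recorded event matters.

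**Conclusion.** The point holds in conditional form. Read naturally, the stated rule treats children lost before 6 months without a recorded event as event-free, and it understates the primary adverse-event rate if such losses occur. For a true 20% rate and an assumed 5–10% loss unrelated to events, the understatement is about 0.5–1.0 percentage points under constant hazards, about 0.2–0.35 if events cluster in month 1, and 1–2 points at most. These figures rest on assumed loss and event rates and on independence between the two. If children leave because an unrecorded problem is developing, the bias could be larger. Neither the crude rate nor a Kaplan-Meier estimate corrects for that, which is why a bound is also needed.

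Nothing here suggests that a safety conclusion would change. This is a cheap improvement to the estimate of the quantity that the primary objective names.

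**What to change.** In Protocol 8.6.1 and 8.7, and in SAP 5.6.1.1 and 5.8:

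1. State that the primary analysis interval is surgery to Visit 4 and that the denominator is all implanted subjects. Define any other intervals used for rates.
2. Beside the crude count and percentage, report the Kaplan-Meier cumulative incidence at 6 months, and at 12 months as supplemental, with 95% CI and censoring at last safety contact. Give it for any adverse event, related adverse events and serious adverse events.
3. State that this estimate assumes loss unrelated to events. Add a worst-case bound that counts each child lost event-free as having had an event.

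Reporting all three event classes also helps with a separate mismatch that must be reconciled: Protocol 8.2.1 defines the primary endpoint as all adverse events and serious adverse events, whereas SAP 5.6.1 limits it to device- and procedure-related events. That choice could move the reported rate more than the denominator does.

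The cost is one extra column, a one-line bound and a slightly less favourable rate. Event start dates are already recorded (Protocol 10.2) and subjects are tracked by visit, so no new data are needed and no planned output is removed.

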## 8.8 Interim Analyses

No formal interim analyses for the purposes of early stopping for effectiveness or for adaptive sample size reestimation are planned. Periodic reports on study progress may be reported to regulatory agencies. Regulatory submission is planned following the collection of the 6-month study data. Data through 12 months will be considered supplemental.

# 9 INFORMED CONSENT PROCESS

The Investigator shall obtain written informed consent from the subject's parent or legal guardian using an approved ICF prior to any clinical investigation-related examination or activity. The rationale of the clinical investigation, as well as the benefits and risks, what participation will involve, and established alternatives to participation will be explained to the subject and their parent or legal guardian in native non-technical language, understandable to the subject. Ample time will be provided for the subject and parent or legal guardian to enquire about details of the clinical investigation and to decide whether to participate.

All questions about the clinical investigation shall be answered to the satisfaction of the subject or the subject's parent or legal guardian. Subjects shall not be coerced or unduly influenced to participate or to continue to participate in a clinical investigation. They shall not waive or appear to waive their legal rights.

Each subject's parent or legal guardian, and the person who conducted the informed consent discussion, shall sign and personally date the Informed Consent Form (ICF). Where required, an independent and impartial witness shall sign and personally date the ICF. A copy of the signed ICF shall be given to the subject. The original signed ICF shall be archived in the Investigator's Site File or subject file at the investigational site.

This process shall be documented in the subject's source documents.

The subject and the subject's parent or legal guardian, shall be informed in a timely manner if new information becomes available that may be relevant to the subject's willingness to continue participation in the clinical investigation. The communication of this information must be documented as an update to the ICF and re-consent of the subject.

